3.8%), and fatigue, abdominal pain lower, lipase increased, amylase increased, alanine aminotransferase (ALT) increased, blood alkaline phosphatase increased, and lymphocyte count decreased (each in 1 subject; 1.9%). Of the 9 subjects (17.0%) who had Grade \geq 3 treatment-related TEAEs, 7 (13.2%) had Grade 3 events, 2 (3.8%) had Grade 4 events (blood CPK increased and autoimmune disorder), and no Grade 5 treatment-related TEAEs were observed. Overall, the TEAE profile was similar across different dose escalation cohorts and the incidences of TEAEs by TEAE category did not increase with increasing dose. In the 1300 subjects comprising the pooled expansion cohort including subjects from 16 tumor expansion cohorts, the most frequently reported TEAEs were fatigue (27.4%), followed by nausea (21.2%), infusion-related reaction (16.2%), diarrhea (15.8%), and constipation (15.7%) (12).

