3.3 Dose-Limiting Toxicity (DLT) Definition

Severity of adverse events will be graded according to CTCAE version 4.03. For the purpose of dose de-escalation, a DLT is defined as any of the following adverse events occurring in the first 56 days following Cycle 1 Day 1 (dosing of PF-04518600 (OX40) and/ or Utomilumab (4-1BB)) of study participation during the dose de-escalation, unless there is a clear alternative explanation (eg, related to underlying disease/ progression):

- Discontinuation of a patient due a toxicity that is at least possibly study drug(s) and/or radiation related before completing DLT period.
- Delay by more than 4 weeks (28 days) in receiving the next scheduled cycle due to persisting toxicities attributable to the study drug(s) and/or radiation.
- Non Hematologic (all will be graded according to CTCAEv4.03 criteria):
 - Grade \geq 3 nausea/vomiting or diarrhea lasting \geq 72 hours while taking optimal supportive medications;
 - Grade \geq 3 fatigue lasting \geq 7 days;
 - Grade \geq 2 pneumonitis lasting \geq 7 days despite treatment with corticosteroids;
 - Grade \geq 3 rash lasting \geq 7 days despite treatment;
 - Grade \geq 3 immune related toxicities lasting \geq 7 days despite treatment with corticosteroids;

- Any other Grade ≥ 3 non-hematological toxicity (except for electrolytes abnormalities that are reversible and asymptomatic or hair loss which is not dose-limiting);
- Grade ≥ 3 AST, ALT, or total bilirubin elevation lasting ≥ 7 days.
- Hematologic:
 - Grade 4 neutropenia [absolute neutrophil count (ANC) $< 500/\text{mm}^3$] lasting ≥ 7 days;
 - Febrile neutropenia (ANC $< 1000/\text{mm}^3$ with a single temperature $\geq 38.3^\circ\text{C}$ or sustained temperature of $> 38^\circ\text{C}$ for over 1 hour);
 - Grade ≥ 3 thrombocytopenia associated with bleeding, or grade 4 thrombocytopenia;
 - Grade 4 anemia.

Elevation of amylase and/or lipase without clinical and/or radiographic evidence of pancreatitis are not considered DLT, and the patient can resume treatment at any grade at the discretion of the treating physician in consultation with the PI.

During the dose de-escalation portion (Arm D) of the study, patients who missed any doses during the DLT period for reasons unrelated to study drug are not evaluable for DLT and will be replaced.

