5.2.4.2 Dose Delays

Patients experiencing Grade 3 or 4 potentially treatment related toxicity or intolerable Grade 2 toxicity despite supportive care should have their treatment interrupted/delayed. Appropriate follow-up assessments should be done until adequate recovery (or until deemed irreversible) occurs as assessed by the Investigator. A treatment delay of more than 4 weeks due to lack of recovery will result in discontinuation of the patient from the treatment, unless continuation (with dose reduction) upon subsequent recovery is considered in the patient's best interest by the investigator (eg, proven clinical benefit).

A new cycle of treatment (or Day 15 of any cycle subject to treatment) may begin only if:

- ANC >/= 1,000/ μ L;
- Platelet count >/= 50,000/ μ L;
- Hemoglobin >/= 8 g/dL;
- Non-hematologic toxicities have returned to baseline or Grade </=1 severity (or, at the investigator discretion, Grade </=2 if not considered a safety risk for the patient).

Withhold scheduled dose for grade >/=3 clinically significant lab abnormality attributed to the treatment. Resume the treatment once the lab abnormality returns to grade </=1. In cases of potential liver injury, consultation with a hepatologist should be considered in the decision to initiate treatment with anti-inflammatory medications.

If these conditions are not met, treatment must be delayed by 1 week. If, after a 1-week delay, all toxicities have recovered within the limits described above, treatment

with study drugs, can be resumed. Both study drugs should be delayed simultaneously if applicable. If the patient has not recovered after 1 week of delay, treatment may be delayed by 1 more week. However, initiation of the next cycle can only be delayed by a maximum of 4 weeks (28 days). Therefore, if persisting toxicity does not allow for the resumption of treatment, the patient will be permanently discontinued.

For all \geq Grade 3 hematological or non-hematological AEs that are NOT study drug-related, at the discretion of the treating physician, study drug dosing may be continued.

Elevation of amylase and/or lipase without clinical and/or radiographic evidence of pancreatitis are not considered DLT, and the patient can resume treatment at any grade at the discretion of the treating physician in consultation with the PI.

For Arm D, patients who experience:

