Adverse events (both non-serious and serious) associated with study drug(s) exposure may represent an immunologic etiology. These adverse events may occur shortly after the first dose or several months after the last dose of treatment. Immunotherapy study drugs (avelumab, utomilumab, and PF-04518600) must be withheld for drug-related toxicities and severe or life-threatening AEs as per Table 8-10 below. Where appropriate, these guidelines include the use of oral or intravenous treatment with corticosteroids as well as additional anti-inflammatory agents if symptoms do not improve with administration of corticosteroids. Note that several courses of steroid tapering may be necessary as symptoms may worsen when the steroid dose is decreased. The dose modification guidelines are intended to be applied when the physician determines the events to be related to one or more of the immunotherapy study drugs (avelumab, utomilumab, and PF-04518600).

For subjects whose dose was withheld due to toxicity, subjects may resume immunotherapy study drug(s) (avelumab, utomilumab, and PF-04518600) upon resolution of toxicity to Grade 0-1 or baseline.

Table 8. Adverse Drug Reactions Requiring Immunotherapy Agent Discontinuation or Modification

In the following table, immunotherapy study drugs or agents refer to avelumab, utomilumab, or PF-04518600.

Any Grade 4 Adverse Drug Reactions (ADRs) require treatment discontinuation with immunotherapy agents (avelumab, utomilumab, or PF-04518600) except for single laboratory values out of normal range that are unlikely related to study treatment as assessed by the Investigator, do not have any clinical correlate, and resolve within 7 days with adequate medical management

Any Grade 3 ADRs require treatment discontinuation with immunotherapy agents except for any of the following:

- Transient (\leq 6 hours) Grade 3 flu-like symptoms or fever, which is controlled with medical management
- Transient (\leq 24 hours) Grade 3 fatigue, local reactions, headache, nausea, emesis that resolves to Grade \leq 1
- Single laboratory values out of normal range (excluding Grade \geq 3 liver function test increase) that are unlikely related to study treatment according to the Investigator, do not have any clinical correlate, and resolve to Grade \leq 1 within 7 days with adequate medical management
- Tumor flare phenomenon defined as local pain, irritation, or rash localized at sites of known or suspected tumor

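### Table 8's discontinuation rule conflicts with Sections 3.3 and 5.2.4.2 for laboratory values judged drug-related, and its laboratory exception gives those values little or no relief

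*Combined protocol and SAP*

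**What the plan says.** Section 5.2.4.3 introduces Tables 8 to 10 by saying that the dose-modification guidelines are "intended to be applied when the physician determines the events to be related" to one or more of the three immunotherapy drugs. Table 8 then sets two base rules:

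- Grade 4: "Any Grade 4 Adverse Drug Reactions (ADRs) require treatment discontinuation with immunotherapy agents", "except for single laboratory values out of normal range that are unlikely related to study treatment as assessed by the Investigator". The excused value must also have no clinical correlate and resolve within 7 days.
- Grade 3: "Any Grade 3 ADRs require treatment discontinuation with immunotherapy agents except for any of the following". The list that follows contains one laboratory item. It leaves out Grade 3 or higher liver tests and covers single values "that are unlikely related to study treatment according to the Investigator, do not have any clinical correlate", provided they return to Grade 1 or lower within 7 days. Amylase and lipase are not named.

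Other sections deal with the same kind of event:

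- Sections 3.3 and 5.2.4.2 both say that amylase or lipase elevation with no clinical or imaging sign of pancreatitis is not a DLT, and that "the patient can resume treatment at any grade at the discretion of the treating physician in consultation with the PI". Neither makes this depend on relatedness.
- Section 5.2.4.2 says that a clinically significant laboratory abnormality of Grade 3 or higher that is attributed to treatment leads to withholding the dose, with resumption at Grade 1 or lower.
- Section 5.2.4.2 also allows dosing to continue, at the treating physician's discretion, through Grade 3 or higher events that are not drug-related.
- Section 3.3 lists as a DLT: "Discontinuation of a patient due a toxicity that is at least possibly study drug(s) and/or radiation related before completing DLT period".

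**The concern.** The laboratory exception depends on a judgement (unlikely related) that sits badly with the table's own scope (judged related). The remaining qualifiers, namely a single value, no clinical correlate and resolution within 7 days, look designed to spare isolated, reversible findings. The relatedness condition largely prevents them from doing so for findings the physician attributes to the drugs. Table 8 then stands as a discontinuation rule against two other instructions that keep such patients on treatment.

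Two things are at stake. First, who stays on treatment: two investigators reading different sections could handle the same event in opposite ways. Second, the primary safety objective in Arm D: because discontinuation can itself be a DLT, an unclear discontinuation rule makes the DLT count unclear. That count feeds the rule accepting no more than 1 of 6 patients with a DLT (Section 3.5) and the early stop of an expansion cohort at an aggregate DLT rate above 33% (Sections 3.3 and 9.2).

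**Working it through.** The plan states no figure on this point, so the check is a comparison of the texts.

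**Step 1: can an event be inside Table 8 and inside its laboratory exception?** A value judged related is in scope but fails the exception's condition. A value judged not related is outside the stated scope, and Section 5.2.4.2 already lets dosing continue for it. Under the scope sentence, little or nothing is left for the exception to cover.

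**Step 2: apply the sections to three events, each judged drug-related.**

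| Event | Table 8 | Sections 3.3 and 5.2.4.2 |
|---|---|---|
| Grade 3 or 4 lipase rise, no pancreatitis | Discontinue; no exception reached | May resume at any grade; not a DLT |
| Other clinically significant Grade 3 laboratory abnormality | Discontinue; exception needs an unlikely relation | Withhold; resume at Grade 1 or lower |
| Grade 3 lymphocyte decrease within 56 days of Cycle 1 Day 1 | Discontinue | Absent from the haematologic DLT list; the catch-all item covers only non-haematological toxicity |

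The first two rows give incompatible instructions for one event. Neither place refers to the other or says which prevails.

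**Step 3: follow the third row into the DLT definition.** The lymphocyte value is not a listed DLT. If Table 8 is followed and the patient stops before the DLT period ends, the discontinuation criterion is met. The event could then count as a DLT only because of the Table 8 action. Section 3.3 lets the principal investigator document why an event that meets the definition is not a DLT, so this outcome is possible but not automatic.

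**Step 4: do such events occur?** Section 1.2.1 describes 53 subjects in the avelumab dose-escalation cohort, 9 of whom had Grade 3 or higher treatment-related events. The terms include "and fatigue, abdominal pain lower, lipase increased, amylase increased". Subject counts by term are autoimmune disorder 3, AST 2, CPK 2 and seven terms at 1 each: 3 + 2 + 2 + 7 = 14. Laboratory terms are AST 2, CPK 2, and lipase, amylase, ALT, alkaline phosphatase and lymphocytes at 1 each: 2 + 2 + 5 = 9 of 14. Lymphocyte decrease occurred in 1 of 53 (1.9%). This shows only that related high-grade laboratory events arise with avelumab. The text does not say whether the values were isolated, without symptoms, short-lived or within 56 days, so no rate of affected patients follows from it.

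**The case against.** The strongest reply is that the protocol, read as a whole, is more flexible than Table 8 alone. Section 5.2.4.3 allows restart after a DLT resolves, lets withheld patients resume at Grade 0–1 or baseline, and permits dose or frequency reduction instead of discontinuation with the IND Office's agreement. Section 7.1.2 does not treat a laboratory value as an adverse event unless it produces symptoms, is clinically significant or needs therapy, so some isolated values may never reach Table 8. An investigator could also read the amylase/lipase sentence as a specific rule that overrides a general one. These points reduce the practical reach. They do not remove the conflict for a clinically significant value judged related: Table 8 says *any*, its list of exceptions is closed, and no precedence is stated.

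Three stronger readings are tempting, and the documents do not support them.

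- *The exception can never be used.* The lead-in to Tables 8–10 also mentions severe or life-threatening events alongside drug-related ones. Table 11 separates unlikely from unrelated. Section 8.6 then asks for a two-way related/unrelated call, and Appendix 1 defines unrelated very strictly. An unlikely event could therefore be recorded as related and still meet the exception.
- *Amylase and lipase elevations become DLTs through the discontinuation criterion.* Section 3.3 itself says that, without pancreatitis, they are not DLTs. The general criterion should not be read as overturning that specific exclusion.
- *The effect on dose decisions can be quantified.* The background counts are not limited to isolated values or to the DLT window, and the documents give no background DLT rate for these combinations.

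**Conclusion.** The inconsistency is real and wrong as written. For laboratory values judged drug-related, Table 8 requires discontinuation, while Section 5.2.4.2 requires withholding and resumption, and Sections 3.3 and 5.2.4.2 allow resumption at any grade for amylase and lipase without pancreatitis. Where a value is judged unrelated, the scope sentence and Section 5.2.4.2 are compatible with continued dosing.

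The consequence for DLT counting is narrower. It concerns values that Section 3.3 neither lists nor excludes, with lymphocyte decrease as the clear example, and it is subject to the principal investigator's documented review. It bears mainly on Arm D, the only arm with a de-escalation phase. Sections 3.2.1 to 3.2.3 describe the new Arm A–C cohorts as already enrolled, and Table 12 reports patients treated in Arms B and C, although Section 9.3 still speaks of expected enrolment.

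No numerical size is given because the documents do not supply the inputs. The conclusion rests on taking the scope sentence and the term adverse drug reaction at face value, and on there being no stated precedence between the sections.

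**What to change.** Reconcile Table 8 with the amylase/lipase sentence in Sections 3.3 and 5.2.4.2, with the withhold-and-resume rule in 5.2.4.2, and with the restart and dose-reduction provisions in 5.2.4.3, so that a related laboratory abnormality has one instruction. Specifically:

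1. Make the relatedness condition in both laboratory exceptions consistent with the table's scope, or remove the exceptions if none is intended.
2. Cross-reference the amylase/lipase rule in Table 8, or state how the two relate.
3. State in Section 3.3 whether a discontinuation that Table 8 requires for an isolated laboratory value counts under the discontinuation DLT criterion.

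Which clinical rule applies is for the sponsor to decide; this point takes no view. The cost is amended wording in Table 8, Section 5.2.4.2 and Section 3.3, with no additional patients, visits or procedures.

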- Change in ECOG PS to \geq 3 that does not resolve to \leq 2 within 14 days (infusions should not be given on the following cycle, if the ECOG PS is \geq 3 on the day of study drug administration)

Any Grade 2 ADR should be managed as follows:

- If a Grade 2 ADR resolves to Grade \leq 1 by the last day of the current cycle, treatment may continue.
- If a Grade 2 ADR does not resolve to Grade \leq 1 by the last day of the current cycle, infusions should not be given on the following cycle. If at the end of the following cycle the event has not resolved to Grade 1, the subject should permanently discontinue treatment with an **immunotherapy agent** ADR (except for hormone insufficiencies, that can be managed by replacement therapy; for these hormone insufficiencies, up to 2 subsequent doses may be omitted).
- Upon the second occurrence of the same Grade 2 ADR (except for hormone insufficiencies that can be managed by replacement therapy) in the same subject, treatment with **immunotherapy agents** has to be permanently discontinued.

Table 9. Treatment Modification for Symptoms of Infusion-Related Reactions

In the following table, immunotherapy study drugs or agents refer to avelumab, utomilumab, or PF-04518600.

NCI-CTCAE Grade	Treatment Modification for Study Drug
Grade 1 – mild Mild transient reaction; infusion interruption not indicated; intervention not indicated.	Decrease the study drug infusion rate by 50% and monitor closely for any worsening. The total infusion time for study drug should not exceed 120 minutes.
Grade 2 – moderate Therapy or infusion interruption indicated but responds promptly to symptomatic treatment (for example, antihistamines, NSAIDs, narcotics, IV fluids); prophylactic medications indicated for ≤ 24 h.	Stop study drug infusion. Resume infusion at 50% of previous rate once infusion-related reaction has resolved or decreased to at least Grade 1 in severity, and monitor closely for any worsening.

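### Table 8's ECOG bullet is misworded or misplaced: as printed, it exempts an unresolved fall to performance status 3 or worse from the Grade 3 stop

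*Combined protocol and SAP*

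**What the plan says.** Table 8 opens its Grade 3 block with "Any Grade 3 ADRs require treatment discontinuation with immunotherapy agents except for any of the following". Five bullets follow:

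- Flu-like symptoms or fever, exempt if they last no more than 6 hours and are controlled.
- A symptom group, exempt if it lasts no more than 24 hours: "Grade 3 fatigue, local reactions, headache, nausea, emesis that resolves to Grade" 1 or lower.
- Single laboratory values, exempt if unlikely to be related, without clinical correlate, and resolved within 7 days.
- "Tumor flare phenomenon defined as local pain, irritation, or rash localized at sites of known or suspected tumor", with no time condition.
- "Change in ECOG PS to \geq 3 that does not resolve to \leq 2 within 14 days", with a bracketed instruction: "infusions should not be given on the following cycle, if the ECOG PS is" 3 or worse on the day of administration.

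The next block of the same table covers Grade 2 reactions. One that persists past the current cycle is held for the following cycle, and then: "If at the end of the following cycle the event has not resolved to Grade 1, the subject should permanently discontinue treatment".

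Outside the table, Section 5.2.4.3 lets withheld drug resume "upon resolution of toxicity to Grade 0-1 or baseline". Section 5.2.4.2 caps the delay at 4 weeks: "if persisting toxicity does not allow for the resumption of treatment, the patient will be permanently discontinued". It also has two routes past that cap. One is the investigator's judgement of best interest upon subsequent recovery. The other is case-by-case continuation after discussion with the Medical Monitor.

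**The concern.** An item on an exception list is something that does not force a stop. Three of the other four items earn that place by being brief or by resolving, and tumor flare earns it by being confined to tumor sites. The ECOG item alone is exempt because it persists. The worse course therefore gets the lighter action.

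Investigators apply this table directly. Two of them could read the bullet in good faith and act differently on the same patient, one following the words and the other the evident purpose of the list. ECOG 3 means limited self-care and more than half of waking hours in bed or chair (Appendix 2), so the choice between stopping and holding matters for that patient. It can also matter for the trial, because Section 3.3 counts a toxicity-related discontinuation within the DLT period as a DLT.

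**Working it through.** The plan states no figure here to reproduce. The check is the logic of the rule, then the timing.

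**1. The rule as printed.** Discontinue if the event is a Grade 3 reaction and is not on the list.

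| Course after a drug-related fall to PS ≥3 | On the list as printed? | Action in Table 8 as printed | Action if the bullet said *resolves* |
|---|---|---|---|
| Not back to ≤2 within 14 days | Yes | Hold while PS ≥3 on the dosing day | Stop |
| Back to ≤2 within 14 days | No | Stop, if handled as a Grade 3 reaction | Exempt |

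Moving the printed wording out of the list as its own stopping criterion would also make the first row a stop.

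**2. When another rule forces a stop.** Inputs: 28-day cycles with doses on Days 1 and 15 (Sections 3.2.1 to 3.2.4), a maximum delay of 28 days (Section 5.2.4.2), onset on cycle day *d* after any dose that day, no other delay, and the decline handled as a persisting toxicity.

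- From the first missed dose, *d* = 1 to 14: (15 − *d*) + 28 = 43 − *d*, which is 42 down to 29 days after onset.
- From the first missed dose, *d* = 15 to 28: (29 − *d*) + 28 = 57 − *d*, again 42 down to 29 days.
- From the next cycle start only, *d* = 1 to 28: 57 − *d*, which is 56 down to 29 days.

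Against a stop at 14 days, these are 29 − 14 = 15 to 42 − 14 = 28 days later, or 15 to 56 − 14 = 42 days later.

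**3. Comparison with the Grade 2 rule.** The end of the following cycle is 28 + (28 − *d*) = 56 − *d*, which is 55 down to 28 days after onset. Counting from the first missed dose, the 4-week limit comes 13 days earlier than this for *d* = 1 to 14 and 1 day later for *d* = 15 to 28. Counting from the next cycle start, it comes 1 day later throughout.

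**4. A case the other rules leave open.** A patient is still at PS 3 on day 15 after onset and at PS 2 on the next dosing day. With nominal dosing every 14 days, one scheduled dose has already fallen while PS was ≥3, so it was held. As printed, the exemption applies and the bracket no longer bars dosing. With *resolves*, the exemption was lost at day 14. Under the resumption rule in Section 5.2.4.3, PS 2 is not baseline, because entry requires ECOG 0-1 (Section 4.1). But Section 5.2.4.2 lets the investigator accept Grade 2 if it is not a safety risk, and no section maps ECOG to a CTCAE grade.

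**5. DLT counts.** The window is 56 days from Cycle 1 Day 1 (Section 3.3). A 14-day stop falls inside it for onset up to study Day 42 (42 + 14 = 56). The 4-week limit, counted from the first missed dose, falls at:

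- Day 43 (15 + 28) for onset on Days 1 to 14;
- Day 57 (29 + 28) for onset on Days 15 to 28;
- Day 71 (43 + 28) for onset on Days 29 to 42.

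So whether a discontinuation falls in the window can depend on the bullet. One event can decide a rule: 1 of 6 is the MTD and 2 of 6 de-escalates (Table 7). For the 33% expansion rule with 14 patients, 4/14 = 28.6% continues and 5/14 = 35.7% stops.

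**The case against.** The strongest reply is that inversion is not proven. Taken as a separate criterion, a decline not recovering within 14 days is a sensible reason to stop, and the extracted text cannot show the original list nesting. That stands as a limit on the diagnosis: the documents do not show whether the word or the position is wrong. It does not rescue the printed rule, because under the stem where it appears the bullet exempts the unresolved course.

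The second reply is that other rules do most of the work, and this largely stands. The bracket bars infusion at PS ≥3, resumption needs Grade 0-1 or baseline, and the delay is capped. Section 6.5 removes patients when adverse event severity indicates a health hazard, or at investigator discretion. The bullet exempts the change in PS and not its cause, so fatigue at Grade 3 beyond 24 hours, for example, is judged on its own line. A reader might infer that a patient who stays at PS 3 can be dosed indefinitely, or that the protocol as a whole is laxer for this patient than for a persistent Grade 2 reaction. The documents support neither: the hold and the cap prevent the first, and step 3 puts the cap between 13 days before and 1 day after the Grade 2 stop.

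The third reply concerns DLTs. Section 3.3 also counts any other Grade 3 or higher non-hematological toxicity, so a decline handled as Grade 3 may already be a DLT, and the principal investigator may reclassify events. The effect on a count is therefore possible, not certain. It cannot be dismissed either, since no section says how a change in PS is graded.

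**Conclusion.** Wrong as written, and a minor safety-wording correction. Within Table 8 the unresolved decline is exempt from the Grade 3 stop and the resolved one is not. None of the limiting rules rewrites the bullet.

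If the decline is handled as a persisting toxicity, the 4-week limit falls 15 to 28 days after a 14-day stop counting from the first missed dose, or 15 to 42 days counting from the next cycle start. Both ranges assume nominal dosing days and no use of the two routes past the 4-week cap. The wording can affect a DLT count in Arm D's 3+3 and under the expansion stopping rule, where the event is not already a DLT by another route.

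The affected group is narrow: a drug-related fall to PS ≥3 with no non-exempt Grade 3 reaction behind it. The documents give no frequency for it. It would go too far to say that the word *not* is certainly the slip, or that DLT counts are in fact distorted.

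**What to change.** The sponsor's clinical team should choose one of two corrections:

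- In the ECOG bullet, replace *does not resolve* with *resolves* and keep the bracketed dosing-day hold. An unresolved decline then loses the exemption at 14 days.
- Keep the wording, move it out of the exception list, and label it a discontinuation criterion.

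Either is a one-line change to Table 8 that can go into the next amendment. Sample size and analysis are unchanged.
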